#### **7.4.7 Plasma Concentrations**

Plasma concentration values will be summarized for the All Treated Population by sampling time point using descriptive statistics, to include the geometric mean and geometric CV (%). The geometric CV is calculated as  $100 \cdot \sqrt{\exp(\sigma^2) - 1}$ , where  $\sigma^2$  is the variance of the log-transformed data. Each subject's plasma concentrations will be plotted over time. For the purposes of plotting the data, plasma concentrations below the limit of quantification (BLQ) that are imbedded between two measurable concentrations will be set to missing; however, BLQ values occurring prior to the first measurable concentration or after the last measurable concentration will be set to zero. For summaries of plasma concentrations, BLQ values will be set to missing. The number and percentage of subjects with BLQ values will be summarized by time point and treatment group.

#### **7.4.8 Pharmacokinetic Analysis**

Pharmacokinetic parameters will be analyzed based on the All Treated Population. For each subject, the PK parameters described in [Section 6.5.3](#) will be determined by a non-compartmental approach when feasible. For the purpose of the non-compartmental PK analysis, all plasma concentration BLQ values occurring prior to the first measurable concentration will be set to zero. BLQ values occurring after the first measurable plasma concentration will be set to missing.

PK parameters will be summarized for the All Treated Population using descriptive statistics that includes the CV. Summaries of  $C_{\max}$  and AUC will also include point estimates for the geometric mean and geometric CV. The geometric mean is calculated by computing the mean of the log-transformed concentration values and then presented in the original scale by calculating the anti-log of the mean result. The geometric CV is calculated as  $100 \cdot \sqrt{\exp(\sigma^2) - 1}$ , where  $\sigma^2$  is the variance of the log-transformed data. Listings of calculated PK parameters will be provided.

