### **DOSAGE AND ROUTE OF ADMINISTRATION:**

Investigational Product (ADU-S100): 800 mcg/lesion (up to 1600 mcg maximum total dose in 2 lesions) administered in a volume of 1.0 mL per lesion by intratumoral injection (injection of visceral lesions per Investigator discretion) on Days 1 and 8 of a 21-day cycle

Standard of Care (pembrolizumab): 200 mg administered by IV infusion on Day 1 of a 21-day cycle per approved product label

---

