#### ***CMIW815X2101/ADU-CL-07***

A total of 47 subjects have been treated with ADU-S100 at doses ranging from 50 to 6400 mcg and evaluated for dose-limiting toxicity (DLT) in the first in human study. Following intratumoral dose administration, ADU-S100 exhibits rapid absorption in the plasma, with  $C_{max}$  achieved right after injection in most subjects. ADU-S100 showed fast clearance in plasma, with mean apparent clearance (CL/F) ranging from 55.9 to 275 L/h and mean elimination  $t_{1/2}$  of approximately 10 to 23 minutes across the dose range of 50 to 6400 mcg. Inter-subject exposure variability was high and exposure of ADU-S100 generally increased with doses increasing from 50 to 6400 mcg.

One DLT has been reported at 6400  $\mu$ g (injection site ulcer). TEAEs, all grades, suspected to be related to study drug, were reported in 36 subjects (76.6%) overall. To date, the most frequently

reported AEs (>10% of subjects) include pyrexia (8 subjects, 17.0%), chills and injection site pain (7 subjects, 14.9%) and headache (6 subjects, 12.8%). Five subjects experienced Grade 3 events including injection site reaction and lipase increased (2 subjects, 4.3%), injection site ulcer, amylase increased, tumor pain and dyspnea (1 subject, 2.1%). One subject experienced a Grade 4 event, respiratory failure (2.1%). No clinically relevant changes of vital and ECG-parameters were observed.

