**Table 5-1 Proposed ADU-S100 Dose Levels**

ADU-S100 Dose	ADU-S100 Total Dose Level 
800 mcg/lesion	Up to 1600 mcg ( maximum dose )
 A maximum of 2 lesions may be injected. ADU-S100 total dose level assumes maximum number of lesions (2) injected; total dose will vary by subject depending on number of accessible target lesions but will not exceed 1600 mcg.	

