**Table 2 ADU-S100 PK Sampling Schedule**

CYCLE	DAY	SCHEDULED TIME (Sampling Window) 
Cycle 1	1	Pre-dose (within 60 min prior to ADU-S100 dosing) Post-dose: 1 h ( $\pm$ 15 min), and 2 h ( $\pm$ 15 min)
	8	Pre-dose (within 60 min prior to ADU-S100 dosing) Post-dose: 1 h ( $\pm$ 15 min), and 2 h ( $\pm$ 15 min)
Cycle 2	1	Pre-dose (within 60 min prior to ADU-S100 dosing) Post-dose: 1 h ( $\pm$ 15 min), and 2 h ( $\pm$ 15 min)

 Post-dose is defined as time from completion of first ADU-S100 intratumoral injection.

The time points specified in Table 2 are applicable to subjects who consented under Protocol Amendment 3 or beyond. Subjects who consented under Protocol Amendment 1 will have the following post-dose sampling time points: 2 min ( $\pm 2$  min), 15 min ( $\pm 2$  min), 30 min ( $\pm 5$  min), 1 h ( $\pm 5$  min), and 2 h ( $\pm 10$  min). Subjects who consented under Protocol Amendment 2 will have the following post-dose sampling time points: approximately 2 min, approximately 15 min, 30 min ( $\pm 5$  min), 1 h ( $\pm 5$  min), and 2 h ( $\pm 10$  min).

When feasible, the following PK parameters will be estimated by non-compartmental methods using actual elapsed time from dosing:

- $AUC_{0-last}$ : Area under the concentration-time curve  $\langle \text{insert unit as concentration unit} \times \text{hours} \rangle$  ( $\text{h} \times \text{ng/mL}$ ) from time zero (pre-dose) to the last measureable concentration, calculated by the linear trapezoidal rule;
- $C_{max}$ : Maximum concentration  $\langle \text{insert unit} \rangle$  ( $\text{ng/mL}$ ), obtained directly from the observed concentration versus time data;

For calculations using the linear trapezoidal rule, the following formula will be used:

$$AUC = \frac{1}{2} (C_1 + C_2)(t_2 - t_1)$$

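### The SAP's PK summaries pool subjects given 800 mcg (one lesion) and 1600 mcg (two lesions) of ADU-S100, with no split by total dose and no dose normalisation

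*SAP*

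**What the plan says.** The protocol synopsis (Dosage and Route of Administration) sets ADU-S100 at "800 mcg/lesion (up to 1600 mcg maximum total dose in 2 lesions". Protocol Table 5-1 adds that "total dose will vary by subject depending on number of accessible target lesions but will not exceed 1600 mcg". Protocol 9.5 allows reduction to 400 and then 200 mcg per lesion. On the dose-exposure relation, the summary of the first-in-human study in Protocol 5.2.2 reports that "Inter-subject exposure variability was high and exposure of ADU-S100 generally increased with doses increasing from 50 to 6400 mcg".

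For the analysis, SAP 7.4.7 states: "Plasma concentration values will be summarized for the All Treated Population by sampling time point using descriptive statistics". SAP 7.4.8 states: "PK parameters will be summarized for the All Treated Population using descriptive statistics that includes the CV". The only grouping named in either section is treatment group, used for counts of values below the limit of quantification, and the trial has one arm (SAP 6.4.2). SAP 7.5.1 summarises total dose received and the number of injected lesions, but does not link them to PK. Individual concentration plots (7.4.7) and listings of PK parameters (7.4.8) are planned.

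On timing, the footnote to SAP Table 2 reads: "Post-dose is defined as time from completion of first ADU-S100 intratumoral injection". No rule covers a second lesion.

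On status, the protocol marks the PK objective as removed by amendment (Section 6) and sample acquisition as removed by Amendment 4 (10.4.3). It says that available PK may be described outside the protocol and its SAP (12.7). The SAP still lists PK as a secondary objective (5.2) and keeps the full analysis.

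**The concern.** A summary pooled over a two-fold dose range answers no clear question. The geometric mean falls between the two dose levels, at a place set by how many subjects happened to have two injectable lesions. The CV, which a reader would take as between-subject variability at a given dose, also contains the dose difference. If lesions are dropped or doses reduced between Cycle 1 Day 1 and Cycle 2 Day 1, the visit-to-visit picture can move for that reason alone. Protocol 7.3 calls this the first trial to inject multiple lesions, so a reader of the PK tables may well want to see one-lesion and two-lesion exposure apart. The planned summary tables do not separate them.

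**Working it through.** **Inputs from the documents.** Dose per lesion 800 mcg, at most two lesions (synopsis; Protocol Table 5-1). Half-life about 10 to 23 minutes (Protocol 5.2.2). Geometric CV = 100·√(exp(σ²) − 1), with σ² the variance of the log values (SAP 7.4.8).

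**Inputs assumed.** Exposure proportional to dose. Share of two-lesion subjects f = 0.25, 0.50, 0.75. The same within-dose log variance s² at both doses. A gap g between the two injections, which the documents do not give.

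**Plan's own figure.** 2 × 800 = 1600 mcg, so the range at full dose is 1600/800 = 2-fold.

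**Pooled geometric mean.** Relative to one lesion it is 2^f: 2^0.25 = 1.19, 2^0.50 = 1.41, 2^0.75 = 1.68. Relative to two lesions it is 2^(f−1): 0.59, 0.71, 0.84.

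**Pooled CV.** Log variance = s² + f(1−f)(ln 2)², with (ln 2)² = 0.480.

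- Mix alone (s² = 0), f = 0.50: 0.25 × 0.480 = 0.120, giving a CV of 35.7%.
- Mix alone, f = 0.25 or 0.75: 0.1875 × 0.480 = 0.090, giving 30.7%.
- Within-dose CV 60%, f = 0.50: s² = ln(1.36) = 0.307; total 0.428; pooled CV 73%.
- Within-dose CV 100%, f = 0.50: s² = ln 2 = 0.693; total 0.813; pooled CV 112%.

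Summarising by dose, or normalising under proportionality, removes the f(1−f)(ln 2)² term and returns the CV to 60% or 100%.

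**Timing in two-lesion subjects.** With first-order decline, the second lesion's contribution at a given nominal time is multiplied by 2^(g/t½). Total concentration relative to simultaneous injection is therefore (1 + 2^(g/t½))/2.

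| Gap g (assumed) | t½ = 10 min | t½ = 23 min |
|---|---|---|
| 2 min | 1.07 | 1.03 |
| 5 min | 1.21 | 1.08 |
| 10 min | 1.50 | 1.18 |
| 15 min | 1.91 | 1.29 |

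Starting the clock at the last injection instead would make the first lesion's dose older than its label. The two-lesion to one-lesion ratio at a given nominal time would then be 1 + 2^(−g/t½). For g = 10 min this is 1.50 (t½ 10 min) or 1.74 (23 min); for g = 20 min it is 1.25 or 1.55. None equals the 2.0 that proportionality implies, so that change replaces one bias with the opposite one.

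**The case against.** The strongest objection is that the PK analysis has been overtaken. Amendment 4 stopped sampling, the PK objective is marked as removed, and Protocol 7.3 speaks of plasma characterisation as part of the initial design. This lowers the weight of the point but does not dispose of it: the SAP still plans the pooled tables, and samples taken before the amendment may still be summarised, here or in a separate document.

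Second, the size rests on proportionality, which the documents do not establish; they say only that exposure generally rose with dose and varied widely. That stands. The 31-36% is the contribution of the mix, not what a reader would see. Against high within-dose variability the visible change is more like 60% to 73%, or 100% to 112%.

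Third, individual plots and parameter listings are planned, so lesion-level information is not lost. A reader might infer that the plan conceals one-lesion versus two-lesion exposure. It does not; the summary tables merely fail to show it.

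Fourth, a reader might infer from the Table 2 footnote that Cmax and AUC are generally mistimed. The documents do not support that. One-lesion subjects are unaffected. Cmax is read from the observed values and uses no time label. For trapezoidal AUC, moving the origin leaves the intervals between post-dose samples unchanged. With a 2 min gap the effect on total concentration is only 1.03-1.07 times. What remains is narrow: the samples at about 2 and 15 min under Amendments 1 and 2 could precede or straddle a second injection.

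Fifth, no formal single-dose versus repeat-dose comparison is planned, and Protocol 9.4.2.2 requires every designated lesion to be injected on each dosing day while that remains possible. A shift in dose mix by Cycle 2 Day 1 is therefore possible but not shown.

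Last, tables by dose would still pool two sampling schedules, with a first post-dose sample at about 2 min or at 1 h. That limit also stands.

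**Conclusion.** The pooling point holds and is minor. As written, SAP 7.4.7 and 7.4.8 give geometric means that describe neither 800 nor 1600 mcg, and CVs that include a dose effect. Under assumed proportionality the mean is displaced by a factor of 1.19 to 1.68 from the one-lesion value for two-lesion shares of 25% to 75%. The CV rises from 60% to 73%, or from 100% to 112%, at a 50% share. The share, the within-dose CV and proportionality are all assumptions; the two-fold dose range is not. Dose reductions could widen that range.

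The documents do not support reading this as a threat to the trial's conclusions, since PK is descriptive and the primary endpoint is response rate. Nor do they support a general timing error: the footnote warrants a flag on a few early samples in two-lesion subjects, not a new time origin.

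**What to change.** Choose one of two routes.

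1. **If PK stays under this SAP.** For the samples already collected, change 7.4.7 and 7.4.8 to summarise concentrations, Cmax and AUC by total ADU-S100 dose given that day (800 mcg; 1600 mcg), with reduced doses listed only. Add dose-normalised Cmax and AUC. Carry the same rule into any separate PK document.
2. **If PK is no longer reported under this SAP after Amendment 4.** Remove 7.4.7 and 7.4.8 so that the SAP matches the protocol.

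On timing, keep the Table 2 definition. In two-lesion subjects, flag any post-dose sample drawn before the second injection was complete, mainly the 2 and 15 min samples of Amendments 1 and 2. Do not restart all times at the last injection. Do not drop flagged samples from Cmax: Protocol 5.2.2 reports that in most subjects the peak came right after injection, so a true peak could be lost.

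The cost is SAP wording and table layout. Lesion-level injection status (SAP 7.4.4.1), total dose (SAP 7.5.1) and the start and stop times of each administration (Protocol 9.4.2.2) are already recorded. The downside is small cells: with about 20 subjects, a 25% two-lesion share leaves 5 in that group (0.25 × 20). That is acceptable for a descriptive display, and the dose-normalised summary keeps the full sample in one table.

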#### **7.4.9 Biomarker Analysis**

Biomarker analysis is outside the scope of this SAP.

### **7.5 Safety Evaluation**

Safety analysis will be carried out for the All Treated Population, to include all subjects who receive at least one dose of either study drug. Subjects who do not complete the study, for whatever reason, will have all available data up until the time of termination included in the analysis. For safety analysis presented by study visit, the baseline value will be defined as the last value reported prior to first administration of either study drug.

#### **7.5.1 Extent of Exposure**

Extent of exposure to study treatment will be summarized for the All Treated Population. The duration of exposure will be presented in days and calculated as the date of last dose of study drug minus the date of first dose of study drug, plus one. The dose intensity will

be calculated as the total dose administered divided by the duration of exposure. Duration of exposure, total dose received (mg for Pembrolizumab; mcg for ADU-S100), and dose intensity will be summarized using descriptive statistics. The number of injected lesions per subject will be summarized.

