### 6.1 Overall Study Design

The ADU-CL-20 study is an open-label, multicenter Phase 2 clinical trial to evaluate the efficacy and safety of intratumoral ADU-S100 (also referred to as MIW815) administered with standard of care treatment (ie, pembrolizumab) in the first-line setting. The multicenter clinical trial will be conducted at approximately 25 sites in North America. Twenty evaluable subjects will initially be enrolled. If the total number responding is greater than or equal to 4, then an additional 14 evaluable subjects will be enrolled in the second stage for a total of 34 evaluable subjects.

The population for this study will consist of adults with metastatic head and neck squamous cell cancer (HNSCC) where pembrolizumab is indicated as the standard of care first line treatment. Individuals with intercurrent illnesses, inadequate organ function, various conditions impacting immune function, or other mitigating factors as detailed in the exclusion criteria will not be enrolled as these factors may interfere with the proposed mode of action of ADU-S100 and pembrolizumab, introduce undue safety risks, or confound interpretation of study results.

The trial design consists of a Screening Period, Treatment Period, and a Follow-up Period as depicted in [Figure 1](#). Screening assessments will be conducted to confirm eligibility and to obtain baseline (pre-treatment) measurements. Screening must be completed within 28 days prior to the first dose of either study drug. An enrollment form will confirm subject eligibility; baseline biopsies will not be performed until enrollment is confirmed. All eligible subjects will receive intravenous (IV) infusions of pembrolizumab (200 mg) and intratumoral injections of ADU-S100 (800 mcg/lesion; up to 2 lesions). During the Treatment Period, study medications will be administered in 21-day dosing cycles until criteria for treatment discontinuation are met, or up to 35 cycles. Tumor responses will be evaluated at 9-week intervals. The Follow-up Period is designed to assess vital status, subsequent anti-cancer therapy, and complete safety reporting requirements.

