**FOOTNOTES FOR TABLE 2-1 (See Sections 9 and 10 for additional information)**

-  Cycle length is 21 days. If a dose of either study drug is delayed, shift scheduled assessments accordingly.
-  EOT Visit occurs 30 days (+7 days) after the last dose of study drug (ADU-S100 or standard of care (pembrolizumab) or prior to commencing new anti-cancer therapy.
-  Follow-up: Visit may be conducted at site or via phone for vital status assessment, any subsequent cancer-related therapies, and safety follow-up to complete required Safety Reporting Periods (Table 10-1), as indicated. Concomitant medications will only be collected if associated with the management of an ongoing AE or SAE, or if a new anti-cancer treatment. Continue imaging if a subject discontinues study treatment for reasons other than progressive disease per Section 10.2.1.
-  Demographics, Medical History, Height: includes date of birth, age, gender, ethnicity, and race. Medical history includes all active conditions and any condition considered to be clinically significant by the Investigator. Disease-specific details include date of diagnosis, primary tumor histology, prior surgery(ies), radiation therapy, chemo- and biological therapies, and stage of cancer. Obtain standing height.
-  Tumor imaging: See Section 10.2.1. Collect scans electronically; perform response assessments per RECIST 1.1 and iRECIST. Tumor assessments should be fixed according to calendar, regardless of treatment delays. After 45 weeks, the imaging frequency for all subjects will be performed at a Q12W (-14 days) frequency until confirmed disease progression, withdrawal, or study end. If a subject discontinues study treatment for reasons other than progressive disease and has not received other anti-cancer therapy, continue imaging at designated frequency. Perform at EOT if more than 6 weeks have passed since last evaluation.
-  Vital Signs: Blood pressure, pulse, respiratory rate, and temperature. Cycles 1 and 2: scheduled time points relative to the start of the pembrolizumab infusion (Day 1) = pre-dose, end of infusion; scheduled time points relative to the start of the ADU-S100 injection (Days 1, 8) = pre-dose, 3 hours and 6 hours post-dose. On all other dosing days, perform vital sign assessment prior to the start of each study drug or more frequently as clinically indicated.

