-  ADU-S100 PK (plasma): Collect blood samples as specified in Table 2-3
-  Plasma cytokines (research), Whole Blood (Transcriptomics): Baseline samples should be collected near the end of screening assessments to avoid unnecessary procedures on individuals who may not meet eligibility. Scheduled time points (Table 2-5) are relative to the start of the ADU-S100 injection. After Cycle 3 Day 1 collect sample on days where tumor imaging indicated. Collect at EOT (or at determination of progressive disease). Collect plasma and whole blood during safety follow-up (only if visit conducted at trial site and not by phone; and subject has not started another anti-cancer treatment).

 Whole Blood (PBMC; select sites only): Baseline samples should be collected near the end of screening assessments to avoid unnecessary procedures on individuals who may not meet eligibility. Collect whole blood for PBMC isolation prior to any study drug administration. Process PBMCs and ship to central laboratory as outlined in the Laboratory Manual. Collect at EOT (or at determination of progressive disease). Collect and process PBMCs during safety follow-up (only if visit conducted at trial site and not by phone; and subject has not started another anti-cancer treatment).

 Tumor Tissue: If no archival tumor sample collected within 90 days prior to start of study treatment is available, then collect fresh biopsy(ies) during Screening and at time points indicated in [Table 2-4](#) (unless subject opts out, site is not amenable to biopsy, or Investigator deems biopsy would pose unnecessary risk). If additional biopsies or relevant samples (e.g. pleural fluid) are collected for routine care during the course of trial or at disease progression, a sample should be retained if possible and submitted for Sponsor research evaluation.

 Pembrolizumab: administer 200 mg by IV infusion on Day 1 of each 21-day cycle as specified in [Section 9.3](#).

 ADU-S100: administer by intratumoral injection on Days 1 and 8 of each 21-day cycle as specified in [Section 9.4](#). Confirm biopsy area has healed prior to initiating dosing.

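### Dose intensity in SAP 7.5.1 leaves the last dosing interval out of its denominator, so it reads above the scheduled rate, most of all in subjects who stop early

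*SAP*

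**What the plan says.** SAP 7.5.1 (Extent of Exposure) gives the whole rule. Duration of exposure is "calculated as the date of last dose of study drug minus the date of first dose of study drug, plus one". Dose intensity is then to "be calculated as the total dose administered divided by the duration of exposure". On reporting it says: "total dose received (mg for Pembrolizumab; mcg for ADU-S100), and dose intensity will be summarized using descriptive statistics". The summary covers the All Treated Population, which SAP 7.2 defines to include anyone given any amount of either drug, so single-dose subjects are in the table.

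The schedule is in the footnotes to the SAP Schedule of Events: "Cycle length is 21 days"; for pembrolizumab, "administer 200 mg by IV infusion on Day 1 of each 21-day cycle"; for ADU-S100, "administer by intratumoral injection on Days 1 and 8 of each 21-day cycle". SAP 6.1 gives 800 mcg per lesion in up to two lesions, with treatment continuing "until criteria for treatment discontinuation are met, or up to 35 cycles".

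Neither the general duration convention in SAP 7.1.4, the list of changes in SAP 7.6, nor the protocol alters the definition. The SAP sets no planned or relative intensity and has no special rule for a subject with one dose. SAP section 4 makes the term study drug interchangeable between the two products, so 7.5.1 does not settle whether first and last dose dates are taken per drug or over both.

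**The concern.** Last minus first plus one is a reasonable description of how long dosing went on. As the denominator of a rate it does not match its numerator: n doses are divided by n − 1 dosing intervals plus one day. The omitted interval matters little over many cycles and a great deal over one or two.

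Dose intensity is the only planned measure that combines dose and time. It is meant to show how far delays, reductions and early stopping eroded the intended exposure, which readers need when they weigh response and toxicity. A rule that inflates the figure most in the least-treated subjects works against that purpose. Early stopping is foreseeable here: the EAS definition in SAP 7.2 provides for subjects who stop for toxicity, clinical progression or death. The first on-study scan is at Cycle 4 Day 1 (Protocol Table 2-1), so an on-schedule subject who stops before that visit has at most three pembrolizumab doses.

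**Working it through.** The documents state no numeric dose intensity, so there is no figure to reproduce. The check compares the SAP formula with the rate implied by the schedule.

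**Inputs**
- Pembrolizumab: 200 mg per 21 days = 9.52 mg/day.
- ADU-S100, per lesion: 2 × 800 = 1600 mcg per 21 days = 76.19 mcg/day.
- Maximum treatment: 35 cycles.

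**Pembrolizumab, n on-schedule doses, dates per drug**

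SAP intensity = 200n / [21(n − 1) + 1]. Divided by 200/21, the ratio to schedule is 21n / [21(n − 1) + 1].

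| Doses | SAP duration (days) | SAP intensity (mg/day) | Ratio to schedule |
|---|---|---|---|
| 1 | 1 | 200 | 21.0 |
| 2 | 22 | 18.18 | 1.91 |
| 3 | 43 | 13.95 | 1.47 |
| 4 | 64 | 12.50 | 1.31 |
| 35 | 715 | 9.79 | 1.03 |

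**ADU-S100, one lesion, k full cycles, dates per drug**

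SAP intensity = 1600k / [21(k − 1) + 8]; ratio = 21k / [21(k − 1) + 8].
- One cycle: 1600/8 = 200 mcg/day, ratio 2.63.
- Two cycles: 3200/29 = 110.34 mcg/day, ratio 1.45.
- 35 cycles: 735/722 = 1.02.
- A single Day 1 injection: 800/1 = 800 mcg/day, ratio 10.5.

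**Dates pooled over both drugs**

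One pembrolizumab dose followed by the Cycle 1 Day 8 injection gives 200/8 = 25 mg/day, ratio 2.63. Pooling shrinks the extreme but does not remove the bias.

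**Delay and reduction**
- Two pembrolizumab doses, the second 14 days late: 400/36 = 11.11 mg/day, 117% of schedule. Counted to the end of the second cycle: 400/56 = 7.14 mg/day, 75%.
- ADU-S100, one lesion, 800 mcg twice in Cycle 1 and 400 mcg (a reduction step in Protocol 9.5) twice in Cycle 2: 2400/29 = 82.76 mcg/day, 109%. Counted over two full cycles: 2400/42 = 57.14 mcg/day, 75%.
- In general, n ≥ 2 pembrolizumab doses with a total delay of d days exceed schedule when 21n > 21(n − 1) + 1 + d, that is, when d < 20. The rule absorbs nearly three weeks of delay before a subject drops below plan.

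**After the correction**

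With last − first + 21 for pembrolizumab, on-schedule intensity is 200n/21n = 9.52 mg/day for every n, ratio 1.00. For ADU-S100, adding 14 days after a final Day 8 injection gives 1600k/21k = 76.19 mcg/day, ratio 1.00. A lone Day 1 injection, counted to cycle end, gives 800/21 = 38.1 mcg/day, or 50% of schedule, which is the share of that cycle's dose actually given.

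**The case against.** The strongest reply is that little depends on this number. No endpoint, stopping rule or exposure–response analysis uses it, and SAP 7.4.6.1 and 7.4.6.6 call the results descriptive. Early stoppers are not concealed either: duration and total dose are summarised alongside, so a one-dose pembrolizumab subject shows 1 day and 200 mg. SAP 7.1.1 adds medians, quartiles and subject listings, 7.4.3 counts delays, and 7.5.2 tabulates adverse events leading to withdrawal, delay, reduction or interruption. All of this stands and limits the consequence, but it does not make the intensity figure right.

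Two stronger readings are tempting, and the documents support neither.
- A reader might infer a 21-fold overstatement for early stoppers generally. That value needs a single pembrolizumab dose and dates taken per drug (or, if dates are pooled, a sole dosing day). It does not apply to ADU-S100 against its scheduled rate, and for pembrolizumab it falls to 1.91 at the second dose.
- A reader might infer that the mean must exceed plan even with delays and reductions. One 21-day delay with k ≥ 2 pembrolizumab doses gives 21k/(21k + 1), just below plan (42/43 = 0.98 for k = 2). ADU-S100 in one lesion over four cycles, at 400 mcg from Cycle 2, gives (1600 + 3 × 800)/71 = 56.3 mcg/day, or 74%. The documents give no distribution of doses received, so the mean could exceed plan but need not.

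The choice of final interval after a lone Day 1 injection is also open to argument. Counting only the 7 days to the next injection gives 800/7 = 114.29 mcg/day, which is 1.5 times schedule. Cycle end is preferable because the scheduled rate is itself defined over the whole cycle.

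**Conclusion.** The point holds. The SAP states a complete rule, and the rule gives an intensity above the scheduled rate for every on-schedule subject. For those with two to four pembrolizumab doses the overstatement is 1.91 to 1.31 times; for ADU-S100 it is 2.63 times after one full cycle and 1.45 after two. It is negligible near 35 cycles, and the 21 and 10.5 values are single-dose extremes. These figures assume on-schedule dosing, dates taken per drug, an unchanged number of injected lesions and the protocol schedule as reference, because the SAP names none.

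The bias is upward and largest in early stoppers. With about 20 evaluable subjects, one of them can move the mean. As an assumed example, one single-dose subject and 19 on-schedule subjects with six pembrolizumab doses (126/106 = 1.19 each) give a mean ratio of (21 + 19 × 1.19)/20 = 2.2, while the median stays at 1.19. The effect is confined to the descriptive exposure summary; ORR and adverse event incidence do not change. It should be corrected because the correction is cheap, not because a trial conclusion depends on it.

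**What to change.** Amend SAP 7.5.1 as follows.
- Keep last dose date minus first dose date plus one as the descriptive duration of exposure.
- For dose intensity, take first and last dose dates separately for each drug and end the denominator at the scheduled end of the cycle containing the last dose. For pembrolizumab this is last − first + 21 days. For ADU-S100 it is last − first + 21 days after a final Day 1 injection, or + 14 days after a final Day 8 injection.
- If a percentage of planned intensity is reported, compute it for ADU-S100 per lesion or against the number of lesions designated for injection. Say how replaced or dropped lesions are counted, since Protocol 9.4.2.3 allows both.

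The denominator change takes about one sentence and a small programming change; the percentage, if wanted, needs a further sentence on lesion count. Dose dates are already recorded (Protocol 9.7), so no new data are needed, and no dose or clinical rule is touched. Reported intensities will be lower than under the current text.
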